4.4 END-OF-STUDY DEFINITION

A participant is considered to have completed the study if he has completed the baseline assessment and the 6-month follow-up assessments.

The end of the study is defined as completion of the 6-month follow-up assessment shown in the Schedule of Activities (SoA), **Section 1.3**.

5 STUDY POPULATION

5.1 INCLUSION CRITERIA

In order to be eligible to participate in this study, an individual must meet all of the following criteria:

1. Age 18 years and older
2. Male
3. Overweight or obesity (body mass index (BMI) $> 25 \text{ kg/m}^2$)
4. Employed >20 hours per week in an occupation classified as blue collar
5. Ability to communicate in English
6. Provision of signed and dated informed consent form

5.2 EXCLUSION CRITERIA

An individual who meets any of the following criteria will be excluded from participation in this study:

1. History of bariatric surgery
2. Diabetes managed with insulin
3. Diagnosis of a serious mental illness
4. Conditions contraindicated to exercise independently (determined using four questions of Physical Activity Readiness Questionnaire)²
5. Report of potentially hazardous alcohol use (ASSIST ≥ 27)¹.
6. Weight loss in the prior six months of 10 pounds or greater
7. Body mass index $\geq 60 \text{ kg/m}^2$, due to increased injury risk with exercise
8. Diagnosis of an eating disorder
9. Any major medical condition that could increase risk for injury or other contradictions for treatment (e.g., cancer treatment) or high likelihood of attrition (e.g., recent hospitalization for depression, psychosis) as determined by the study team

5.3 LIFESTYLE CONSIDERATIONS

During this study, participants are asked to:

- Refrain from starting medications or dietary supplements for weight or appetite control and
- Refrain from participating in another weight loss program.

5.4 SCREEN FAILURES

During this study, participants are asked to:

- Attend an in-person assessment visit and complete questionnaires online.
- Attend at least one treatment session.

Participants who do not complete the baseline assessment visit will not be randomized into the study.

5.5 STRATEGIES FOR RECRUITMENT AND RETENTION

Participants will be recruited via the postcards mailed to their homes. They will be directed to a study website where a brief description of the study will be presented. Participants recruited through the four recruitment messages will be sent to separate but identical websites. Participants who are interested will be asked to complete an online screening form. Those who appear initially eligible will be contacted to schedule a time to attend a study orientation. This orientation will allow participants the opportunity to gain information about the study and to experience the web conferencing platform (if they have not used it before). The session will describe the study and will use the motivational interviewing approach described by Kiernan and colleagues ^{44, 45, 46} to enhance engagement and retention to the study. Following this, participants will attend an in-person assessment visit where they will sign consent before completing the physical measures and self-report questionnaires. Participants who complete the baseline visit and measures will be randomized to receive either the tailored intervention or the generic intervention following a 1:1 randomization ratio.

Recruitment will be supplemented by recruitment through flyers, notices on a hospital "on-hold" line, and online recruitment messages as needed. These potential participants will be encouraged to contact the study through the study website and will go through the recruitment process described above.

All recruitment materials and plans will be reviewed and approved by the Rush University Institutional Review Board prior to implementation.

To maximize retention, we will collect multiple methods for contacting participants (e.g., email, telephone) at baseline. Participants will tentatively schedule their follow-up assessment during their initial treatment session, a method we have used in prior studies to increase retention rates. During the intervention, participants have not engaged with treatment for at least one anticipated sessions will be contacted directly by intervention staff to encourage reengagement with the program.

Guidelines for attempting to schedule intervention visits. These general guidelines are intended only to set norms around how frequently attempts should be made to contact participants for intervention visits. Each attempted contact should be tracked in Research Electronic Data Capture (REDCap). Unlike scheduling outcomes assessments, clinical judgment can play a larger role in determining how “aggressively” interventionists should seek to communicate with participants. In general, it is likely most effective to adopt a non-judgmental tone, normalize the difficulty a participant may be having with engaging in the intervention, and invite participants to outline when and how we can stay in touch with them until they are hopefully able to reengage with the study.

WHAT TO TRY

Call and/or email participants the day after missed session and encourage their return to group the following week.

Increase variability and/or frequency of attempts to every 3-4 days, while trying to not overwhelm the participants using calling, text or email.

Send a letter asking them to get in touch

Call from Principal Investigator to probe for concerns or barriers to engagement

WHEN TO TRY IT

When first session is missed

After 1 week of no contact with study (e.g., no session attendance or self-monitoring reported)

No contact for 3-4 weeks

When deemed appropriate, but no later than 5 weeks overdue

6 STUDY INTERVENTION(S) OR EXPERIMENTAL MANIPULATION(S)

6.1 STUDY INTERVENTION(S) OR EXPERIMENTAL MANIPULATION(S) ADMINISTRATION

6.1.1 STUDY INTERVENTION OR EXPERIMENTAL MANIPULATION DESCRIPTION

Recruitment substudy

During recruitment for the trial, we will test the effects of recruitment messages using mailing postcards with four different recruitment messages to addresses of men believed to work in blue-collar occupations. The intervention exposure is the receipt of the postcards by potential participants. The four recruitment messages:

- Standard recruitment message alone (e.g., “Tradesmen: Boost your energy and feel better through changes to eating and physical activity!”)
- Standard message plus messages to enhance trust (e.g., “Join the BELT study: built for tradesmen with tradesmen” and “Why we are doing this: Our team wants to understand how to help men like you improve their health. We’ve developed a new program with input from men like you for men like you. It’s designed to fit into your life!”),
- Standard message plus an endorsement from a prior participant (“This is a great program...safe, thoughtful, and effective.”)
- A combined trust and endorsement message.

An identical description of the program plus a call to action “Go to [study website] to see if you are eligible!] will be included in all postcards. Participants will be sent to separate but identical websites to allow us to track the reach of the messages via the number of independent website visits. The remaining recruitment process will be identical for all participants, regardless of recruitment message received. From the website, participants can choose to be screened for eligibility and will be randomized into the trial as appropriate.

The BELT Intervention

The BELT intervention will be delivered via 16- group session conducted via web-conferencing (i.e., Zoom) supported by short, educational videos hosted on the study website. Online groups sessions will allow participants to give and receive social support from peers while also minimizing disruption to lifestyle that would be needed for a face-to-face group session. Study staff will help troubleshoot any issues using this system during the intervention. Importantly, all participants will have chance to use the platform during the online orientation session for the study. Group sessions will be 60 minutes per session and will occur weekly for months 1-3, twice in month 4, and once a month in months 5 and 6.

Group sessions will be accompanied by short videos that participants will view asynchronously that align with the topics discussed in the group sessions. These videos will be used in lieu of traditional printed handouts. Short videos can be an efficient way to convey the educational materials and is a familiar approach to participants who may have viewed educational on workplace safety in the past. Videos will

be short (maximum of 3 minutes) to encourage participants to view the videos regularly. Similar to previous men-only weight loss interventions, these will feature straight forward language, include humor, and will include a conversational style of speech. New videos will be posted at least once each week to encourage participation with the program throughout the 6-month study. Scripts for videos will be developed simultaneous to the leader guides for the groups sessions to ensure overlap between topics. The intervention guides and scripts will be developed to take an autonomous support approach (e.g., present multiple options for participants to choose from in making changes).

The lessons in this study focus on target behaviors and skills that will aid participants in reducing their intake below their baseline levels (see topics in Table). The behaviors and skills align with what we used in our earlier study. These were identified by reviewing the literature and finding specific activities that have either been associated with weight loss in past studies—for example, reducing caloric beverages can produce weight loss over time⁴⁷ or behaviors that have been targeted in other successful weight loss studies.^{48 49} The goal of selecting these specific behaviors was to select behavioral targets that can be articulated to participants in a simple manner, monitored in a simple manner, and implemented with minimal lifestyle disruption. The behaviors that were expected to yield the greatest caloric reductions will be presented first. This is designed to help participants to begin to lose weight earlier in the intervention in order to prevent discouragement. Four additional lessons that focus on weight loss maintenance skills will be presented during months four through six. These lessons ("Relapse Prevention", "Eating in Social Situations", "Slips, Slides, and Falls", and "Maintaining Your Momentum") are skill based versus focusing on specific eating behaviors. These topics were selected for use during the tapered contact period of the program because these are skills that support making long-term changes to eating and exercise behaviors.

Eating behavior

Participants will be encouraged to make several small changes to their diet throughout their day. Rather than providing calorie goals to stay beneath, participants will be encouraged to use the "tools" (i.e., specific eating behaviors or change techniques) presented during group sessions and videos. Examples of these tools include: reducing portion sizes, replacing with a lower calorie option, removing extras, skipping extra servings. Starting during the second group meeting, participants will be asked to identify aspects of their eating and physical activity habits that are not aligned with their desire to lose weight and that they were willing to change. Based on this self-evaluation, participants will be asked to set weekly goals for eating behaviors they wanted to change. As part of the self-evaluation, participants will be given an estimate of their daily caloric needs as well as the prescribed intake level to produce a one-to two-pound weight loss per week based on their weight and level of physical activity reported during their baseline assessment. Participants will be given a list of upcoming lesson topics and a description of the behaviors that indicate tools that may be useful strategies to help them lose weight (see Table X). Taking an autonomy supportive approach, participants will be asked to consider which behaviors they would be most willing to change and which behaviors they are not ready to change, emphasizing their autonomy in the program.

Physical activity

Goals for leisure-time physical activity will be matched across interventions groups at 150 minutes of moderate-to-vigorous physical activity per week. In the BELT condition, participants will be given progressive exercise plans (starting at 0, 50, 100 minutes of activity per week) that encourage exercise 5 days per week and will increase by 5 minutes per exercise session until the goal is reached. A distinction will be made between occupational activity and leisure-time physical activity with an emphasis on the health benefits associated with leisure-time activity.

Goal setting

At the end of each group session, participants will set a SMART goal (Specific, measurable, attainable, relevant, time-bound) that they will strive to achieve over the next week. These goals will be encouraged to focus on the behavior topic presented in the group session or another behavior of interest.

Self-monitoring

BELT will use a simplified approach to self-monitoring where participants will be encouraged to monitor (at a minimum) their daily weight, minutes of leisure-time physical activity, and the “tools” participants used to modify their eating that day.

Participants will be encouraged to track this information using the diary section within the MyFitnessPal app. The study will create accounts within the app for participants that will give the intervention team access to the self-monitoring information. The team will log into the platform and email feedback on participant progress (e.g., monitoring completeness, weight loss, progress towards eating and activity goals). Participants will also use the MyFitnessPal app to closely monitor their intake during week 1 of the program. Continued detailed self-monitoring will be presented as a tool participants can use to help increase weight loss as needed but will not be required.

BELT Lesson Topics

| Session | Topic Title/Primary Video | Secondary video | Topics covered |
|---------|---|--------------------------|--|
| 1 | Lifestyle change for weight control | Self-monitoring 101 | Energy balance, weight loss goals, self-monitoring to increase nutrition knowledge |
| 2 | 3RS: Replace, reduce, remove, skip seconds: Your everyday tools | Self-weighing as a tool | Self-regulation process; introduction to tools for weight loss; motivation for weight loss |
| 3 | Balance your beverages | SMART goals | Beverages; goal setting for self-regulation |
| 4 | Preventing snack attack | Hungry, bored, or habit? | Excess calories from snacks, choosing healthier snack options, evaluation of hunger as eating cue (vs. other cues) |

| | | | |
|----|--|--|--|
| 5 | Move more! | Do I have to exercise if I work all day? | Exercise principles (FITT), exercise safety, goals, the importance of leisure-time PA |
| 6 | Portion distortion | Nutrition facts or fiction? | Reading nutrition labels, estimates of portion sizes, how to reduce portions using stimulus control |
| 7 | Reduce in restaurants | Quick and easy meals on the go* | Eating in restaurants and on the go |
| 8 | Increase to decrease | Plan your plate | Tips for incorporating more fruits and vegetables into diet; introduce balanced plate with half fruits/vegetables |
| 9 | Cutting the fat | Winning with water | Reduce fat intake to reduce caloric density; cutting empty calories from fat; revisit beverage concepts and ways to increase water consumption |
| 10 | Start with breakfast | Breakfast FAST!* | Importance of maintaining regular eating patterns; suggestions for breakfast alternatives |
| 11 | Swap out sweets | Grab and go at the gas station | Reduce calories from sugar. Healthier alternatives when buying on the go |
| 12 | Fitness fights fatigue | Round out your routine | Reducing sedentary behavior to make time for PA; including stretching and resistance training to activity routine |
| 13 | Eating in social situations | Get the help you need | Social cues for eating and how to manage them; Identifying places where social support can help with example scripts |
| 14 | Do you know your zone? Problem solving | | Self-regulation for relapse prevention; check in on concerns about transitions to independence; encourage problem solving around weight loss |
| 15 | Slips, Slides, and Falls | Rework what's around you | Relapse prevention; stimulus control |
| 16 | Maintaining your momentum | | Maintaining motivation during maintenance |

*Written recipes will be provided instead of videos for these topics

DPP GLB

The Diabetes Prevention Program Group Lifestyle Balance program⁵⁰ will be used as the comparator in this study. The first 16 lessons will be covered over 16, hour-long group sessions conducted online via Zoom. The intervention will be minimally modified from the published version except to make the program appropriate for online delivery (e.g., no supervised exercise sessions). The published behavior targets will be used (e.g., calorie and fat goals set by beginning weight). The lessons will be provided to

participants as PDF files. These lessons will be minimally modified (e.g., remove reference to pedometers).

Comparison of BELT to the DPP GLB

| | BELT | DPP GLB |
|-----------------------|--|---|
| Contact | 16 60-minute group sessions conducted over Zoom | 16 60-minute group sessions conducted over Zoom |
| Educational materials | Pocket guide + videos | PDF handouts |
| Dietary goals | Small changes to eating behaviors | Moderate changes to diet |
| Physical activity | 150 minutes of leisure-time physical activity | 150 minutes of leisure-time physical activity* |
| Self-monitoring | Daily tracking of weight, physical activity, and tools used to change eating | Daily tracking of weight, physical activity, and calories (after session 6) |

*Note. This is change from the DPP GLB as published due to the difficulties of providing pedometers during a remotely delivered program.

6.1.2 ADMINISTRATION AND/OR DOSING

Participants in both randomized groups will be encouraged to attend weekly group sessions months 1-3, two sessions in month 4, 1 session in month 5, and 1 session in month 6. All group sessions will be one hour in duration.

6.2 FIDELITY

6.2.1 INTERVENTIONIST TRAINING AND TRACKING

The program interventionist is an registered nurse with many years of experience delivering behavior change interventions. Prior to the intervention beginning, the PI and interventionist will develop (BELT) or review (DPP GBL) all group leader guides. The PI and interventionist will meet weekly to review the previous week's sessions and review the next sessions materials.

A subset of group intervention sessions will be audio recorded and reviewed by the primary investigator using a treatment fidelity checklist. The investigator will monitor for contamination of the tailored program material appearing in the standard program but not vice versa. A subset of feedback provided to participants will also be reviewed for contamination and completeness.

6.3 MEASURES TO MINIMIZE BIAS: RANDOMIZATION AND BLINDING

Randomization to treatment conditions for the recruitment message substudy will be conducted by the study Principal Investigator using a random number generator. Participants will not be blind to the study condition but will be blind to hypotheses. Staff cannot be blinded to study arm as they will need to ask which recruitment message was received.

In the main trial, randomization to treatment condition will be conducted by a statistician not involved with treatment delivery. Randomization will be revealed to participants at their first treatment session. Outcome assessors will be blind to treatment assignment.

Though it is not possible to blind participants to the nature of the treatment they are receiving, both arms will be named and described as (and truly are) active treatments to eliminate expectancy effects. As both arms will receiving information remotely, risk of contamination is minimal.

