3 OBJECTIVES AND ENDPOINTS

| OBJECTIVES | ENDPOINTS | JUSTIFICATION FOR ENDPOINTS |
|--|--|--|
| Primary | | |
| Aim 1: Examine the acceptability of tailored behavioral weight loss program and a standard program in men working in blue-collar occupations. | Participant reported satisfaction with program acceptability at 3 months. | Participant satisfaction is a proxy for program acceptability. |
| Aim 2: Compare recruitment approaches that vary on trust-based messaging to recruit men with overweight/obesity who work in blue-collar occupations. | Proportion of participants who enroll in study by recruitment message type. | The goal of recruitment is enrollment in the study. Using the proportion of participants who received the postcard as the endpoint provides an assessment of the effectiveness of the message. |
| Secondary | | |
| Determine the feasibility of retaining participants to a randomized trial over six months. | Percentage of participants who complete a weight assessment at the 6-month assessment timepoint. | High retention to the study will indicate the study procedures are feasible for a fully powered trial. |
| Determine the reach of recruitment messages. | Number of visits to recruitment websites. | The website is the first indication of participant interest in the study. |
| Determine the acceptability of the intervention. | Participant reported satisfaction with program at 6 months. | |
| Tertiary/Exploratory | | |
| Determine percentage of participants who achieve a clinically significant weight reduction (5% of initial weight). | Weight objectively assessed by study staff at baseline, 3 months, and 6 months. | 5% weight loss is an established indicator of clinically significant weight loss. |
| Evaluate participants perceptions of program components. | Semi-structured interviews. | We will conduct semi-structured interviews with participants to gain a deeper understanding of their perceptions of program components and their experiences in the program. |

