4 STUDY DESIGN

4.1 OVERALL DESIGN

This study is a two-armed randomized controlled trial with assessments at baseline, 3 months after randomization, and 6 months after randomization. The objective is to assess the acceptability of the intervention to participants at 3 months and the feasibility of study procedures at 6 months with retention to the study as the outcome. This is a single site, Stage 1 study.

Participants will be randomly assigned to study groups by a biostatistician who is not involved with the study assessments or interventions using a random number generator. Individuals will be randomly assigned to study conditions in cohorts of approximately 30 individuals. Randomization will be concealed from participants until their first treatment session.

Participants will be randomized to receive either the tailored BELT (Better Energy through Lifestyle for Tradesmen) treatment or a standard weight loss program (Diabetes Prevention Program Group Lifestyle Balance; DPP GLB). The groups will be matched on number of weeks of treatment, mode of delivery, and contact time.

During recruitment for this study, we will conduct a randomized comparison of recruitment messages. This comparison will use a factorial design testing the effects of enhancing trust in the researchers (Trust Messaging: Yes, No) and the effects of a participant endorsement (Endorsement: Yes, No). Names and addresses for individuals from a purchased marketing list will be randomly assigned to be sent a postcard with a recruitment message matching their assigned condition. Recruitment reach will be assessed through website visits and number of participants responding to each message.

This is a feasibility study with no formal hypotheses to be tested.

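### Section 6.3 leaves recruitment-substudy staff unmasked to message for a reason that is not a true constraint, so those who influence enrolment, the Aim 2 primary outcome, may know the message beforehand

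*Combined protocol and SAP*

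**What the plan says.** Section 3 gives the Aim 2 primary endpoint as "Proportion of participants who enroll in study by recruitment message type", and section 9.4.2 compares the proportions randomised with a chi-square test. On blinding in this substudy, section 6.3 says: "Staff cannot be blinded to study arm as they will need to ask which recruitment message was received". No other reason is given. The blinding of outcome assessors in the same section belongs to the main trial and concerns treatment assignment, not message.

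Several staff steps lie between the website and randomisation. Section 5.5 says: "Those who appear initially eligible will be contacted to schedule a time to attend a study orientation". That orientation uses a motivational interviewing approach and is followed by an in-person consent and baseline visit. Exclusion 9 in section 5.2 covers conditions that raise injury risk or make attrition likely, "as determined by the study team".

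On how a man's message can be known, section 4.1 says: "Names and addresses for individuals from a purchased marketing list will be randomly assigned to be sent a postcard". Section 5.5 adds: "Participants recruited through the four recruitment messages will be sent to separate but identical websites". Section 10.1.1.2 has men submit contact information with the online screening form. Section 6.1.1 states that the rest of the recruitment process will not differ by message.

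**The concern.** In most trials the people whose knowledge of allocation matters are those who measure the outcome. Here the outcome is enrolment itself, so the people who matter are those who follow men up, encourage them at orientation and decide on a judgement-based exclusion. If they know the message, effort or discretion can differ by message without anyone intending it. The resulting difference in enrolment would look like a message effect, and the chi-square test cannot separate the two.

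The comparison is meant to inform recruitment for this and future studies (section 4.2), so a distorted estimate could be carried forward. The protocol presents the lack of masking as unavoidable, although its own design offers other ways to learn each man's message.

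**Working it through.** **Step 1. Is asking necessary?** Set the sections side by side.
- Section 6.3: staff must ask, so they cannot be blinded.
- Sections 4.1 and 10.1.1.2: each named addressee has a message before mailing, and contact details arrive with the online screening form. Matching the two gives the assigned message.
- Sections 5.5 and 6.1.1: each message leads to its own website, from which men go to screening. A site code on the form would give the message of entry. The stated purpose of the sites is counting visits ("separate but identical websites to allow us to track the reach of the messages"); a link from site to form is not described and would have to be added. The list match does not depend on it.

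The message can therefore be obtained without asking.

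**Step 2. Can staff affect the outcome before it is fixed?** Website visits and the online screen come before staff contact. Scheduling, orientation, the consent visit and exclusion 9 come after it and before randomisation. The answer is yes, for the later part of the path.

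**Step 3. How sensitive is the comparison?** The plan's own figure comes first: 15 per group × 2 interventions × 2 cohorts = 60 (section 9.2), which reproduces. The substudy has 4000 addressees less returned postcards (section 9.3).

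Assumptions, for illustration only: equal allocation, no returned postcards, all 60 men enrolled by postcard, no true message effect, two-sided 0.05. The documents state no alpha. Enrolment is then 60/4000 = 1.5%, or 30 of 2000 at each level of a factor.

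For counts a and b out of 2000 each, the uncorrected chi-square on 1 df is (a − b)² / [(a + b)(1 − (a + b)/4000)]. With a + b = 60 the denominator is 60 × 0.985 = 59.1.

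| Men shifted | Counts | Ratio | Chi-square | p |
|---|---|---|---|---|
| 2 | 32 v 28 | 1.14 | 16/59.1 = 0.27 | 0.60 |
| 3 | 33 v 27 | 1.22 | 36/59.1 = 0.61 | 0.44 |
| 4 | 34 v 26 | 1.31 | 64/59.1 = 1.08 | 0.30 |
| 7 | 37 v 23 | 1.61 | 196/59.1 = 3.32 | 0.069 |
| 8 | 38 v 22 | 1.73 | 256/59.1 = 4.33 | 0.037 |

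If fewer men enrol by postcard, fewer shifts suffice: 7 of 40 (27 v 13, p = 0.026) or 5 of 20 (15 v 5, p = 0.025).

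**Step 4. The same question as conversion rates.** Staff cannot change a man's message, only whether he enrols, so the shifts can be restated. If half of eligible men convert (assumed), 30/0.5 = 60 are eligible per level. Conversion of 55% v 45% gives 33 v 27. Conversion of 60% v 40% gives 36 v 24. In a simulation of 40,000 runs, the chance of p<0.05 with no message effect was 0.12 and 0.34 respectively, against 0.05 with equal conversion. At an assumed 75% conversion (40 eligible per level), 80% v 70% gives 32 v 28 and a chance of 0.08; 85% v 65% gives 34 v 26 and 0.18. None of these conversion gaps comes from the documents.

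**The case against.** A reader might infer that the staff who judge eligibility and run orientation will certainly know each man's message. The documents do not say so. Section 6.3 refers to staff in general and does not say who asks or when; the question could come at the end. What stands is that no role is exempted and no timing is set, so they may know.

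A reader might also infer that enrolment will be biased in favour of the enhanced messages. That is not supported either. Section 4.2 describes all four messages as ones the team thinks may work. A team filling 60 places has reason to enrol every eligible man, and section 6.1.1 commits to the same process throughout. That commitment counts, but no safeguard is described for keeping it. Exclusions 1 to 8 rest on history, diagnosis, screening score or measurement, so the discretionary element of eligibility is narrow.

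Asking also has a plausible use. Men who come through flyers, the on-hold line or online notices are sent through the same process (section 5.5), and their source must be known. They fall outside the 4000 addressees, however, and the question can sit in the online form out of staff view.

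Finally, this is a feasibility study with no formal hypotheses (sections 4.1 and 9.1), and shifts of 2 to 4 men would not reach nominal significance. That limits the consequences. It does not remove the point, because the comparison is named as primary, is tested, and would be read for its size.

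**Conclusion.** The concern holds in a limited form. The plan accepts that staff may know the message while they can still influence the Aim 2 primary outcome, and the reason it gives is not binding on its own design. The documents do not show that screening and orientation staff will know, or that any bias will arise; its size and direction are unknown.

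The risk is mainly to the estimate. Under the assumptions above, a few men handled differently would give a spurious ratio of 1.14 to 1.31, while a nominally significant result would need about 8 of 60. The main trial's comparison of the two programmes is not affected. This is a cheap correction that should be made, not a flaw that invalidates the substudy.

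**What to change.** Replace the sentence in section 6.3 with these provisions:
- The assigned message is obtained by matching the man to the randomised mailing list and/or from a site code attached to the online screening form.
- It is held in a field hidden from screening, orientation and consent staff until the man is randomised or closed as not enrolled.
- A named role not involved in screening or orientation holds the key. This needs stating because the Principal Investigator generates the message allocation.
- Men recruited by flyer, on-hold notice or online message are coded as non-postcard and lie outside the 4000-addressee population.
- Any question about which postcard a man saw is asked only after randomisation, as a check.

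The cost is a little data-management work: the list match, the site code if used, and a restricted field in whichever data-capture system (section 10.1.3 allows two) holds the screening form. No sample size or analysis changes. Masking will be imperfect, since a man may mention the postcard in conversation.
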